12.3.5. Sub-Analysis for Sling Repair and Interventions for Recurrence

12.3.5.1. Subjects with only POP repair and those with sling and prolapse repair

A two sample t-test will be performed in pain score change from baseline to each follow-up visit within mesh or native tissue repair group, to compare groups with and without SUI

surgery. Using this method of analysis will make it less difficult to assess causality for adverse events, including pain.

12.3.5.2. Subjects with office-based intervention for recurrence

Adverse procedural/device event rates and QOL information will be collected for 36 months, regardless of whether or not the subject has office-based intervention for recurrence.

Event rate for each of device-related or procedure-related adverse events of specified AE type (mesh erosion, mesh exposure, dyspareunia) during the period after the intervention will be summarized by treatment group. Treatment groups will be compared using Cox regression for the event-free survival time (starting at the time of first office based intervention) with treatment arm.

For each QOL instrument, a comparison using a t-test will be performed between native tissue repair and mesh group on the basis of QOL score at the first scheduled follow-up after office-based intervention for recurrence.

A two sample t-test will be used to compare groups with office-based intervention for recurrence and without intervention within each treatment group. QOL score change will be reported from the last follow-up visit before office-based intervention for recurrence, to the next scheduled follow-up visit after office-based intervention for recurrence within each treatment group. For those subjects without recurrence, we will use baseline as the “before” time point in analysis, and the QOL data at 6 month follow-up visit as the “after” time point.

Similarly, event rate for each adverse device and procedure-related event type specified (mesh erosion, mesh exposure, dyspareunia) will be compared between subjects with office-based intervention for recurrence and those without. This will be done using a Cox regression of time to the first onset of each adverse event after the starting time to compare groups with office-based intervention for recurrence and within each treatment group. The starting time will be baseline for those subjects without intervention, and time of office-based intervention for recurrence for those with intervention.

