Propensity score adjusted confidence intervals described in Section 12.2.3 (Propensity Score Methodology) will be used to evaluate continuous variables including QOL score improvements between two groups.

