12.2.2. Control of Systematic Error/Bias

To reduce selection bias in this non-randomized study, each study center will be permitted to enroll subjects in only one of the treatment groups. Physicians will be selected based on device and clinical research experience and the decision as to which device to implant in subjects prior to study initiation at each center. Some study centers may be permitted per Boston Scientific to enroll subjects in both treatment and control groups. All decisions will be documented prior to subject enrollment. All subjects meeting the eligibility criteria at the study center will be screened and enrolled as applicable.

Propensity score stratification will be utilized to address the potential imbalance in risk factors between groups, described in Section 12.2.3 (Propensity Score Methodology). This analysis will be performed blind to all clinical outcome data and prior to performing any analysis of endpoints.

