12.2.3. Propensity Score Methodology

Analyses comparing the treatment groups will be adjusted for the propensity score. The propensity score is the probability that the subject enrolled in the mesh arm rather than the native tissue (control) arm, given the characteristics of the subject and center. The characteristics identified are as follows: age, race, body mass index, smoking, diabetes, post-menopausal, prior prolapse repair, prior hysterectomy, estrogen use, POP-Q C measurement, POP-Q Ba measurement, POP-Q Bp measurement, concomitant repair for stress urinary incontinence, and surgeon case volume. Logistic regression of both treatment arms (i.e., (transvaginal mesh repair vs. native tissue repair) on these characteristics will be used to estimate the propensity score. The subjects will then be partitioned into five strata

corresponding to quintiles of the propensity score. If the balance between treatment arms within the strata is deemed adequate, the treatment difference adjusted for propensity score stratum will be estimated as described in the following.

The propensity adjusted treatment difference will be based on averaging the treatment differences of the propensity score strata. For a binary outcome, the within-stratum treatment difference is $D_j = p_{Tj} - p_{Cj}$, where p_{Tj} and p_{Cj} is the proportion of treatment and control subjects, respectively, in stratum j . The variance of D_j is approximately

$$V_j = \frac{p_{Tj}(1 - p_{Tj})}{n_{Tj}} + \frac{p_{Cj}(1 - p_{Cj})}{n_{Cj}}$$

Denoting the number of subjects in stratum j by $n_j = n_{Tj} + n_{Cj}$, the treatment difference will be estimated by the (weighted) mean of the within-stratum treatment differences

$$D = \sum_j \frac{n_j}{n} D_j$$

where $n = \sum_j n_j$ is the total sample size across all strata and study arms. D is approximately normally distributed with variance

$$V = \sum_j \left(\frac{n_j}{n}\right)^2 V_j$$

from which a confidence interval for the true treatment difference will be constructed. For each continuous outcome, the confidence interval will be constructed similarly, with D and V obtained as above with the treatment difference within each stratum replaced by $D_j = \bar{X}_{Tj} - \bar{X}_{Cj}$, where \bar{X}_{Tj} and \bar{X}_{Cj} , respectively, is the mean of the treatment and control subjects, and

$$V_j = \frac{S_{Tj}^2}{n_{Tj}} + \frac{S_{Cj}^2}{n_{Cj}}$$

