12.3.1. Rate of Office-Based Intervention for Recurrence

Statistical testing will be performed to determine if the rate of office-based intervention for recurrence in the treatment group will be superior to the control group. The null hypothesis is that the rate of office-based intervention for recurrence in treatment group is greater than or equal to the rate in control group:

$$H_0: \pi_{treatment} - \pi_{control} \geq 0$$

The alternative hypothesis is:

$$H_a: \pi_{treatment} - \pi_{control} < 0$$

where $\pi_{treatment}$ and $\pi_{control}$ are the office-based intervention rates for recurrence in treatment group and control group respectively. The rejection of null hypothesis indicates the superiority of the treatment group over the control group.

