12.3.5.3. Subjects with surgical intervention for recurrence

The above mentioned analyses for the subgroup with office based intervention for recurrence will be repeated for subjects with surgical intervention for recurrence.

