12.3.7. Sub-Analysis for Interventions for Complications

The above sub-analyses in Section 12.3.5 will be repeated for re-surgery for complications or recurrence.

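### Mesh is compared with native tissue only among women who needed a later intervention, so a difference there cannot be read as an effect of the repair; the tests named also conflict with the plan's propensity rule

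*Combined protocol and SAP*

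**What the plan says.** Section 12.3.5.2 makes two between-arm comparisons restricted to women who had an office-based intervention for recurrence. The first is on quality of life: "a comparison using a t-test will be performed between native tissue repair and mesh group on the basis of QOL score". It is done instrument by instrument and uses the next scheduled visit once the intervention has taken place. For mesh erosion, mesh exposure and dyspareunia, "Treatment groups will be compared using Cox regression for the event-free survival time", with the clock starting at the first intervention and treatment arm as the only term named. Neither method mentions the propensity score, a baseline covariate or the pre-intervention score.

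Section 12.3.5.3 says the analyses "will be repeated for subjects with surgical intervention for recurrence". Section 12.3.7 says: "The above sub-analyses in Section 12.3.5 will be repeated for re-surgery for complications or recurrence". Section 12.1.2.3 separately lists a comparison of adverse event rates between arms among women with re-surgery.

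The general rule in Section 12.2.3 is: "Analyses comparing the treatment groups will be adjusted for the propensity score". No exception is stated. Section 12.2.2 gives the reason: "Propensity score stratification will be utilized to address the potential imbalance in risk factors between groups". Sections 12.1.2.3, 12.3.2, 12.3.4 and 12.3.6 invoke Section 12.2.3 explicitly for other between-arm analyses. Section 12.3.5 does not.

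Section 12.3.1 tests "if the rate of office-based intervention for recurrence in the treatment group will be superior to the control group", and Section 12.3.2 does the same for surgical intervention for recurrence. Nothing in the plan labels the subset comparisons descriptive or warns that the subsets are formed after treatment.

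**The concern.** Needing an intervention is itself an outcome of the repair. If the rates differ by arm, as Sections 12.3.1 and 12.3.2 hypothesise for recurrence, the women who enter the subset from each arm have been filtered differently. They need not be comparable even if the arms were comparable at surgery.

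Two features of the design add to this. Section 11.5 leaves re-surgery to physician and subject discretion, and Sections 8.2 and 12.2.2 have most centres enrolling one arm only. Local thresholds for intervening are therefore entangled with arm. In addition, the t-test uses the score after intervention rather than a change from an earlier score, so any difference in severity at entry passes straight into the comparison.

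A difference in QOL or in adverse event hazard after intervention could then be reported as a property of mesh when selection alone could produce it. Separately, an analyst who follows Section 12.3.5.2 and one who follows Section 12.2.3 would run different analyses.

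**Working it through.** **The plan's own figure.** Section 12.3.5.2 gives no sample size, power or intervention rate. The nearest inputs are the primary effectiveness assumptions in Section 12.1.1.2: success 70% for native tissue and 85% for mesh, two-sided 0.05, power 90%. The unpooled formula gives (1.960 + 1.282)² × (0.70×0.30 + 0.85×0.15) / 0.15² = 157.6, so 158 per arm and 316 in total, as stated. The 165 evaluable per arm in Section 8.1, divided by 0.8, gives 206.25, so 207 per arm and 414 in total, as stated.

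**Selection model (assumption).** Give both arms the same standard normal latent severity and the same after-effects. A proportion q, those above the upper-q point z, have the intervention. Mean severity among them is φ(z)/q. The documents give no intervention rate for recurrence, so a range is shown. The 30% v 15% row uses composite failure rates as a stand-in, and the other rows are assumed.

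| Native v mesh rate | Mean severity, native | Mean severity, mesh | Gap (mesh minus native) |
|---|---|---|---|
| 30% v 15% | 1.159 | 1.554 | 0.395 SD |
| 15% v 7.5% | 1.554 | 1.887 | 0.333 SD |
| 10% v 5% | 1.755 | 2.063 | 0.308 SD |
| 6% v 3% | 1.985 | 2.268 | 0.283 SD |
| 30% v 30% | 1.159 | 1.159 | 0 |

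The gap in QOL is this gap times the severity-QOL correlation. At an assumed correlation of 0.5 it is 0.395 × 0.5 = 0.20 SD in the first row and 0.283 × 0.5 = 0.14 SD in the 6% v 3% row.

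**Same model, other reading.** Section 11.5 defines recurrence by a state: prolapse beyond the hymen with bulge symptoms. If QOL tracks how far a woman is past that threshold, the relevant quantity is the mean excess, φ(z)/q − z.
- At 30% v 15%: 1.159 − 0.524 = 0.63 for native and 1.554 − 1.036 = 0.52 for mesh.
- At 6% v 3%: 1.985 − 1.555 = 0.43 for native and 2.268 − 1.881 = 0.39 for mesh.

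The mesh women are now slightly less severe, so the sign reverses.

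**Effect on the t-test.** This was simulated with 165 randomised per arm, identical after-effects and 5000 runs, under the first reading. The subset holds about 0.30 × 165 = 50 native and 0.15 × 165 = 25 mesh women in the 30% v 15% case. Rejection rates at nominal 5% were:

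| Severity-QOL correlation | 30% v 15% | 15% v 7.5% |
|---|---|---|
| 0 | 5% | 5% |
| 0.3 | 8% | 6% |
| 0.5 | 14% | 8% |
| 0.7 | 28% | 13% |
| 0.9 | 63% | 29% |

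With equal rates (30% v 30%, correlation 0.7) the rejection rate was 5%.

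**Would baseline adjustment cure it?** Suppose the measured baseline score correlates 0.5 with latent severity (assumption). At 30% v 15% and severity-QOL correlation 0.7, regression adjustment for that score cut the spurious gap only from 0.28 to 0.26 SD and the rejection rate from 28% to 25%.

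**Subset size.** At the assumed 6% v 3% of 207, there are about 12 native and 6 mesh women. Five strata leave 6/5 = 1.2 mesh women per stratum, too few for the within-stratum variance in Section 12.2.3. At 12 v 6 women and 0.14 SD, the t-test rejects about 5.8% of the time.

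**The case against.** Several points on the other side stand.

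- A reader might infer that these comparisons are planned without any propensity adjustment. The documents do not support that flatly. Section 12.2.3 has a blanket rule, so the fault is a conflict between two sections.
- A reader might infer a bias against mesh. That direction comes from one modelling choice, and the mean-excess calculation reverses it. Any gap in this model also needs unequal intervention rates and a link between severity and outcome.
- The 30% v 15% figures are failure rates on the three-part composite. They are not intervention rates. At the smaller assumed rates the false-positive inflation is negligible, and sparse data are the main limitation.
- For complications, which Section 12.3.7 also covers, the plan gives a single anticipated rate per intervention type and tests non-inferiority (Sections 12.3.3 and 12.3.4). At equal rates the model predicts no gap.
- No magnitude has been worked out for the Cox comparison. Erosion and exposure are mesh events, so the selection argument there concerns dyspareunia.
- Section 12.3.5 is headed as a sub-analysis, with no stated hypothesis, margin or power. Adjusted contrasts in all women are planned elsewhere.

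None of this makes the subset comparison interpretable. For recurrence, the plan itself hypothesises unequal rates, allocation is not randomised, and no text limits the tests to description. Applying the Section 12.2.3 rule would settle the conflict but would not remove selection on a later event.

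**Conclusion.** The concern holds in a limited form. The between-arm t-test and Cox comparison among intervened women mix selection into the subset with any effect of the repair, and the plan offers no means of separating the two. The methods named in Section 12.3.5.2 also conflict with the general rule in Section 12.2.3.

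The bias cannot be sized from the documents. The 0.28 to 0.40 SD severity gap rests on a normal threshold model, a two-to-one ratio of intervention rates, and QOL that follows overall latent severity. It must still be multiplied by an unknown correlation. A reader might go on to conclude that the trial's main findings are at risk, but the primary effectiveness and safety analyses do not use these subsets and are unaffected.

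**What to change.** In Sections 12.3.5.2, 12.3.5.3 and 12.3.7, and in the re-surgery item of Section 12.1.2.3, remove the between-arm t-test and Cox test among intervened women. Present those subsets by arm with number of women, mean scores, event counts and follow-up time. State that they do not support a causal comparison of mesh with native tissue. This also removes the conflict with Section 12.2.3.

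Rest between-arm inference on contrasts already planned in all ITT women with propensity adjustment: QOL (Sections 12.1.2.1 and 12.1.2.3) and intervention rates (Sections 12.3.1 to 12.3.4).

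Do not substitute an all-women endpoint of intervention followed by an adverse event. It would mix how often women are treated again with what happens afterwards. With few events, the Section 12.2.3 variance would be zero in any stratum-arm without an event, making the interval too narrow.

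The cost is SAP and protocol wording. The downside is that no between-arm p-value is reported within the intervened subsets.

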⁵Assessment of Risk Factors includes menopausal status, estrogen use, age, smoking, diabetes status, BMI, hysterectomy status, concomitant procedures, surgeon training and experience.

⁶All serious and non-serious device, procedure, and pelvic floor-related events, any other relevant events pertaining to the pelvic region, and any events resulting in death will be collected.

⁷Every effort should be made to do the follow-up visit within the window; however, if this is not possible, the site should attempt to complete the visit as soon as possible but before the next visit window opens. Follow-up visits will be considered missed once the visit window for the next follow-up visit opens. For the Month 36 visit, the visit is not considered missed until the last day of the visit window.

If a subject requires a re-surgery during the study, please refer to the reduced table below for follow-up assessments. Subjects undergoing re-interventions (non-surgical) continue with the study schedule as noted in Table 11.1-1. Additional data will be collected on subjects requiring a re-surgery, including a second procedure, mesh removal (as applicable), and second hospital discharge. All subjects who are re-operated on will continue with their follow-up schedule until 36 months post their initial study procedure.

Table 11.1-2: Data Collection Schedule for Subjects Requiring a Re-Surgery

Procedure/Assessment	Screening/ Enrollment Visit	Pre- Operative/ Baseline Visit	Surgery	Discharge	Post-Operative Follow-up Visits (± 4 Weeks)				
					Month 2 Visit (± 4 Weeks)	Re-Surgery	Discharge	Next Scheduled Follow-up Visit (-4/+12 weeks)	Month 36 Visit** (-4/+12 weeks)
Informed Consent	X							After a re-surgery, subjects will return to the clinic on the date of their next regular study visit per the Schedule of Events table above. Subjects will continue to return for all scheduled Follow-up Visits until 36 months post their initial study procedure.	
Inclusion/Exclusion Criteria Review	X								
Demographics		X							
Urine Pregnancy Test	X	X							
Physical Examination		X							
Medical History ¹		X							
Pelvic Exam with vaginal length measurement		X			X				X
Assessment of infection (vaginal, bladder)				X	X		X		X
Prolapse Grading (POP-Q Scoring)		X			X				X
PFDI-20 (Pelvic Floor Symptoms)		X			X				X
PFIQ-7 (Quality of Life)		X							X
PISQ-12 (Sexual Functioning)		X							X
PGI-I for Prolapse (Patient Improvement)									X
TOMUS Pain Scale		X			X				X

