11.4.7. Months 6, 12, 18, 24, 36 Visits (-4/+12 weeks)

- Pelvic exam with vaginal length measurement
- Assessment of infection (vaginal, bladder)
- Prolapse grading (POP-Q Scoring)
- Assessment of pain (TOMUS pain scale) and analgesic intake
- PFDI-20
- PFIQ-7
- PISQ-12

- PGI-I for Prolapse
- SSQ-8 for surgical satisfaction (Months 6, 12, 24, 36 only)
- EQ-5D for health status (Months 12, 24, 36 only)
- Assessment of adverse events (device, procedure, or pelvic floor related)
- Assessment of risk factors
- Study completion (Month 36 only)

All subjects who have completed the study surgery and discharge will proceed to be followed through the above-outlined study visits to Month 36 where the primary endpoint analysis will be achieved when the last subject completes this visit. All subjects completing the Month 36 visit will be considered to have completed the study.

11.5. *Re-Intervention/Re-Surgery*

It is the intention of this study to demonstrate an improvement in anterior/apical pelvic organ prolapse through clinical effectiveness of a transvaginal prolapse repair kit. However, it is recognized that during the course of the study, there is a possibility subjects may require a medical re-intervention for events including but not limited to failed prolapse repair, persistence of prolapse symptoms, or a mesh or procedure-related complication. A re-intervention may include surgical or non-surgical treatments and can occur for a medical complication or for prolapse recurrence. For the purpose of this study surgical interventions shall be classified as “re-surgery” and non-surgical interventions shall be classified as “re-interventions”. Analyses will be performed to compare the rate of office-based interventions and of surgical interventions for medical complications and for prolapse recurrence in both treatment groups.

Non-surgical interventions (re-interventions) are defined as office-based procedures and do not involve an operating room procedure. Examples of non-surgical interventions may include but are not limited to an office visit to trim exposed mesh or suture in the vagina, a pessary, or physical therapy to treat procedural complications or persistent prolapse symptoms. Data on non-surgical interventions will be captured in the CRFs. Subjects will continue to be followed per the regular study visit schedule.

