Surgical interventions (re-surgery) are surgical operations performed to correct recurring prolapse symptoms, a procedural complication, or a mesh-related complication. These surgical events typically may occur on an outpatient basis yet can require admission to a hospital. The decision to perform a re-surgery for failed prolapse repair or persistence of prolapse symptoms will be per physician and subject discretion and all re-surgery data will be captured in the Case Report Forms. All subjects defined as having a prolapse recurrence will be those who have anatomic and symptomatic failure of their prolapse surgery (prolapse beyond the hymen and symptoms of vaginal bulge).

Subjects undergoing a re-surgery will be followed to 36 months post their initial study procedure as indicated in Table 10.1-2. The subject should return to the clinic for the next regular study visit as per her original schedule. If the subject elects to not undergo re-

surgery, then the subject will be followed to the Month 36 visit unless the subject chooses to withdraw consent from the study. No subject will be followed for more than 36 months beyond their initial study procedure.

11.6. *Subject Death*

If any serious adverse event results in death (regardless of the relatedness to the study device, procedure, or pelvic floor), the event is to be documented in the source documentation, Case Report Form, and reported to the Sponsor within the timeframe noted in Table 21.7-1 (Investigator Reporting Requirements). If an autopsy is conducted, a copy of the final autopsy report should be submitted to the Sponsor or designee. The primary objective of the autopsy is to determine the cause of death, complications and other relevant findings.

12. Statistical Considerations

12.1. *Endpoints*

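### The QOL sub-analyses after re-surgery take the next scheduled visit with no minimum interval, so time since surgery varies from days to 12 months while women without recurrence are scored at Month 6

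*Combined protocol and SAP*

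**What the plan says.** Section 12.3.5.2 is written for office-based intervention for recurrence. For each QOL instrument it compares the arms by t-test "on the basis of QOL score at the first scheduled follow-up after office-based intervention for recurrence". Within each arm it also compares women with and without the intervention. For women with it, the change runs from the last visit before the intervention "to the next scheduled follow-up visit after office-based intervention for recurrence within each treatment group". For women without recurrence, the change runs from baseline, with "the QOL data at 6 month follow-up visit as the “after” time point".

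Section 12.3.5.3 says that these analyses "will be repeated for subjects with surgical intervention for recurrence". Section 12.3.7 says that the sub-analyses of 12.3.5 "will be repeated for re-surgery for complications or recurrence".

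The visit calendar is not reset by an operation. Section 11.5: "The subject should return to the clinic for the next regular study visit as per her original schedule". Table 11.1-2 (Section 11.1): "After a re-surgery, subjects will return to the clinic on the date of their next regular study visit". PFDI-20 and the TOMUS pain scale are collected from Month 2, and PFIQ-7 and PISQ-12 from Month 6 (Sections 11.4.6 and 11.4.7). All four then recur at Months 12, 18, 24 and 36.

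The plan sets no minimum interval after re-surgery, no adjustment for time since re-surgery and no exclusion of early scores.

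**The concern.** Section 11.5 defines office-based interventions as not involving an operating room; its examples are trimming exposed mesh, a pessary and physical therapy. Taking the next visit after such a procedure is reasonable. Carried unchanged to operations, the same rule accepts a score taken a few days after surgery, including a score on a pain scale.

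The comparator adds to the difficulty. Women without recurrence contribute a change measured at a nominal 6 months after their index surgery. Re-operated women contribute a change measured at whatever interval the calendar leaves. The within-arm t-test therefore mixes any effect of recurrence and re-surgery with time since the last operation. The mesh versus native tissue comparison in re-operated women carries the same mixture in both arms, and is distorted if the two arms are re-operated at different points of the calendar.

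**Working it through.** The plan gives no figure for the interval between re-surgery and the after score, so there is nothing to reproduce. The interval follows from the visit grid once a timing for re-surgery is assumed.

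**Inputs from the documents.** Scheduled visits at Months 6, 12, 18, 24 and 36 (Section 11.4.7), original dates kept (Section 11.5, Table 11.1-2), comparator at Month 6 (Section 12.3.5.2).

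**Assumptions, not in the documents.** Re-surgery times are uniform over months 2 to 36, and visits fall on target dates. Six weeks = 6 × 7/30.44 = 1.38 months.

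**Current rule.** The gap is the next scheduled visit minus the re-surgery time. The intervals between visits have lengths 4, 6, 6, 6 and 12 months, total 34.

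- Within 6 weeks: 5 × 1.38/34 = 20%.
- Within 2 months: 5 × 2/34 = 29%.
- Less than the comparator's 6 months: (4 + 6 + 6 + 6 + 6)/34 = 28/34 = 82%.
- Mean gap: (4² + 3 × 6² + 12²)/(2 × 34) = 268/68 = 3.9 months.
- Mean squared gap: (4³ + 3 × 6³ + 12³)/(3 × 34) = 2440/102 = 23.9, so SD = √(23.9 − 3.94²) = 2.9 months.
- Range 0 to 12 months. Root-mean-square distance from 6 months: √(2.9² + (6 − 3.94)²) = 3.6 months.

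**Other timing assumptions.** Share of after scores within the stated time of re-surgery:

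| Instruments and re-surgery timing | 4 wk | 6 wk | 8 wk | 12 wk |
|---|---|---|---|---|
| PFIQ-7/PISQ-12, even over 0–36 months | 13% | 19% | 26% | 38% |
| PFIQ-7/PISQ-12, even over 0–24 months | 15% | 23% | 31% | 46% |
| PFIQ-7/PISQ-12, even over 24–36 months | 8% | 12% | 15% | 23% |
| PFIQ-7/PISQ-12, even over 0–36, visits spread over −4/+12 weeks | 11% | 17% | 23% | 36% |
| PFDI-20/TOMUS (adds Month 2), even over 0–36 months | 15% | 23% | 31% | 44% |
| PFDI-20/TOMUS, even over 0–24 months | 19% | 29% | 38% | 54% |
| Re-surgery 0.5–3 months after a scheduled visit | 0% | 0% | 0% | 0% |
| Re-surgery 1–4 months after a scheduled visit | 0% | 0% | 0% | 19% |

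**With a 2-month floor** (first scheduled visit at least 2 months after re-surgery), under the same even timing over months 2 to 36:

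- Re-surgery after month 34 has no qualifying visit: 2/34 = 6%.
- The remaining 32 months split into lengths 2, 6, 6, 6 and 12, with gaps of 2–4, 2–8 (three times) and 2–14 months.
- Mean gap: (2 × 3 + 18 × 5 + 12 × 8)/32 = 192/32 = 6.0 months.
- Mean squared gap: [(4³ − 2³) + 3 × (8³ − 2³) + (14³ − 2³)]/(3 × 32) = 4304/96 = 44.8, so SD = √(44.8 − 36) = 3.0 months.
- Root-mean-square distance from 6 months falls from 3.6 to 3.0. The SD does not fall.

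**Number of women.** The only re-surgery rate given is about 1%, for complications (Section 12.3.4): 0.01 × 165 = 1.7 to 0.01 × 207 = 2.1 per arm. No rate is given for re-surgery for recurrence.

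**The case against.** The strongest case against is that the size is unknown and may be trivial. The documents give neither a recovery period nor the timing of re-surgery. Section 11.5 defines recurrence as anatomic plus symptomatic failure, and POP-Q is scheduled at study visits. If re-surgery usually follows such a visit by one to four months, no after score falls within 8 weeks. This stands: a reader might infer that many scores are taken during surgical recovery, and the documents do not support that. But nothing ties re-surgery to visits; Section 11.5 leaves the decision to physician and subject. Even on the visit-triggered pattern, re-surgery 0.5 to 3 months after a visit leaves 3 to 5.5 months to the next one, or 9 to 11.5 months after Month 24, so the unequal timing remains.

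A reader might also note that under even timing (4 + 4 × 5)/34 = 24/34 = 71% of after scores fall within 5 months, the lower edge of the Month 6 window, and call that the share in recovery. The protocol does not say that Month 6 was chosen because women are still recovering before it.

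Nor do the documents show that the arm comparison is biased. That needs re-surgery timing to differ between mesh and native tissue, and they give no evidence on this. A contrast of early complications with late recurrences could not arise in 12.3.5.3, which covers recurrence only.

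Finally, re-operated women continue all visits to Month 36, and Section 12.1.2.3 lists an assessment of QOL after re-surgery that is not confined to the first visit. This limits the harm. It does not repair the comparisons in 12.3.5.3 and 12.3.7, which name the first or next visit.

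**Conclusion.** The point holds as a defect of definition in two sub-analyses. A rule suited to office procedures is applied to operations without a minimum interval, so the after score may come from days to 12 months after re-surgery and is set against a Month 6 score in women without recurrence. Some after scores may therefore be taken soon after an operation: about a fifth within 6 weeks and 29% within 2 months under even timing, and possibly none if re-surgery closely follows a visit. These shares rest on assumed timing.

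The within-arm comparison with women without recurrence is affected most. The mesh versus native tissue comparison is affected only if timing differs by arm. The women may be few, and neither primary endpoint is involved. It is a minor point, worth correcting because the correction is cheap.

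**What to change.** In Sections 12.3.5.3 and 12.3.7, for re-surgery only, define the after value for all QOL instruments as the first scheduled visit at least 2 months after re-surgery. Two months matches the first postoperative QOL collection in the index schedule. Report time since re-surgery by arm beside every result, and keep the first-visit version as a sensitivity analysis. Leave the office-based rule of 12.3.5.2 as it is. No visit moves and no care changes.

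The cost is analysis-plan wording and, under even timing, about 6% of re-operated women without an after value. The floor removes the earliest scores and brings the mean interval from 3.9 to 6.0 months, close to the comparator. It does not narrow the spread (range 2 to 14 months, SD about 3), so the results must be read with the reported timing.

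A longer floor of 5 months is not advised. By the same method the usable 29 months split into lengths 5, 6, 6 and 12 with mean gaps of 7.5, 8, 8 and 11 months. The mean interval becomes (37.5 + 96 + 132)/29 = 9.2 months (range 5 to 17), 5/34 = 15% of after values are lost, and the root-mean-square distance from 6 months rises to 4.4, worse than under the current rule.
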